- History of Inflammatory bowel disease
- Familial adenomatous polyposis syndrome (FAP)
- Hyperplastic polyposis syndrome
- Referral for incomplete colonoscopy or polyp clearance

Randomization:

Once a patient has been screened to ensure inclusion and exclusion criteria have been met and has provided consent for participation in the study, the subject will be randomized in a 1:1 ratio. Randomization outcomes include the Standard Colonoscopy or the EndoRings Colonoscopy.

Statistical Analysis & Sample Size:

The primary analysis compares the adenoma detection rate between the EC group and the SC group. It is assumed that the proportion of patients with at least one adenoma would be 25% with SC and 35% with EC colonoscopy.

A two group Chi-Square test with a 0.05 one-sided significance level will have 80% power to detect a difference of 10% ADR between the two groups (odds ratio of 1.615) when the sample size in each group is 259, a total sample size of 518 subjects.

The final sample size will be 569 after adding the 10% expected drop-out rate.

Interim analysis will be performed after the 200th patient is enrolled to assess device performance and protocol amendment.

Data Integrity and Safety

All paper charts pertaining to the patient will be kept under lock and key in coordinators office away from the endoscopy area. The data entry will be performed into an excel file which will be stored on an internal network drive with encryption and password security. Only approved personnel by the IRB will have access to the file storage. This file will also not have any identifiable patient information. A study log with the identifiable information will be kept in a separate folder to enable the investigators to assist in any research audit. No procedural data except the date of examination will be entered into this log.

Any subject who wishes to withdraw from this investigation on his/her own accord and for whatever reason is entitled to do so without obligation and prejudice to further treatment. In addition, the Investigator may decide for reasons of medical prudence, to withdraw a subject. In either event, the Investigator will clearly document the date and reason(s) for the subject's withdrawal from this investigation in the CRF and should indicate whether or not he considers it was related to the study interventions.

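### Does a final sample size of 569 fall short of covering the stated 10% drop-out?

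*Combined protocol and SAP*

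**What the plan says.** The section Statistical Analysis & Sample Size assumes that the proportion of patients with at least one adenoma "would be 25% with SC and 35% with EC colonoscopy". The test is described as "A two group Chi-Square test with a 0.05 one-sided significance level", and the plan says that it "will have 80% power to detect a difference of 10% ADR" "when the sample size in each group is 259, a total sample size of 518 subjects". The next sentence sets the enrolment target: "The final sample size will be 569 after adding the 10% expected drop-out rate". The section Randomization gives equal allocation ("the subject will be randomized in a 1:1 ratio").

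The document gives no inflation formula and no other enrolment target. It does not say whether the 10% is a share of the patients enrolled or of the patients required, and it does not define the population for the primary analysis.

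**The concern.** A drop-out allowance is there so that the required number remains after the losses. A drop-out rate is usually read as a share of those enrolled, so the usual step is to divide the required number by one minus the rate. Multiplying by one plus the rate is a familiar shortcut that always gives a smaller total.

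Here 569 sits close to 518 × 1.10 and below 518 / 0.90, so the plan seems to have taken the shortcut. On that view the trial would finish with fewer than 518 evaluable patients if drop-out ran exactly as expected, and the quoted 80% power would not quite be met. Starting from the printed 518, the product is 569.8, so 569 can also look as if it had been rounded the wrong way.

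**Working it through.** **Inputs**, all from Statistical Analysis & Sample Size: p₁ = 0.25 (standard colonoscopy), p₂ = 0.35 (EndoRings), difference δ = 0.10, one-sided α = 0.05, power 80%, drop-out 10%. Allocation is 1:1, from Randomization.

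**1. Reproduce the base figure.** The pooled two-proportion formula without continuity correction is

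n = [z₀.₉₅ √(2p̄(1−p̄)) + z₀.₈₀ √(p₁(1−p₁) + p₂(1−p₂))]² / δ²

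with p̄ = 0.30, z₀.₉₅ = 1.645 and z₀.₈₀ = 0.842. The two square roots are √0.42 and √0.415, and the result is n = 258.62. This rounds up to 259 per group, 518 in total, as the plan states. The odds ratio (0.35 × 0.75) / (0.25 × 0.65) = 1.615 also agrees. Any question therefore lies in the drop-out step alone.

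**2. Read the drop-out sentence as adding 10% to the requirement.**

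- From the rounded total: 518 × 1.10 = 569.8, which gives 569 if truncated and 570 if rounded up.
- From the unrounded requirement: 2 × 258.62 × 1.10 = 568.96, which rounds up to 569.

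The document does not show which route was taken. The second gives 569 with correct rounding, so no slip is established on this reading.

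**3. Read 10% as a share of enrolled patients, all lost to the primary analysis.**

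- Enrolment that leaves 518 on average: 518 / 0.90 = 575.6, so 576, which is 7 more than 569.
- Evaluable patients from 569: 569 × 0.90 = 512.1, about 256 per group and 518 − 512.1 = 5.9 short.

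**4. Translate the shortfall into power.** Power = Φ{[δ√n − z₀.₉₅ √0.42] / √0.415}.

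| Evaluable per group | Power |
|---|---|
| 259 | 80.05% |
| 256 | 79.6% |

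The loss is about 0.4 percentage points. Exact binomial calculation gives 80.01% and 79.72%, a smaller loss still.

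**5. Compare with the uncertainty in drop-out itself.** With 569 enrolled and the evaluable patients split equally:

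| Drop-out among enrolled | Power |
|---|---|
| 5% | 81.5% |
| 10% | 79.6% |
| 12% | 78.9% |
| 15% | 77.6% |

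If the true rate is 10%, the number dropping out of 569 has standard deviation √(569 × 0.10 × 0.90) = 7.2, which exceeds the shortfall of about 6. Enrolling 576 would leave at least 518 evaluable with probability of only about 56%, because it covers the expected loss and no more.

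**The case for a change.** The case for a correction is that this one sentence sets the enrolment target, and a reader who takes drop-out as a share of enrolled patients cannot reconcile 569, 10% and 518. The word adding may explain how the number arose without making it adequate for its purpose. Even from the unrounded requirement, division gives 2 × 258.62 / 0.90 = 574.7, above 569. A clearer sentence would cost nothing and need no extra patients.

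Much of this stands. Division is the better practice when every drop-out is lost to the analysis, and an allowance for drop-out makes little sense unless at least some are lost. The denominator is indeed left unstated.

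It does not stand that 569 is wrong however the sentence is read, because adding 10% to the unrounded requirement gives 569 exactly as rounded. Nor is the loss of all drop-outs a given: the provision for withdrawal under Data Integrity and Safety requires the date and reason to be documented but does not say whether a withdrawn patient's data are excluded. Describing 569 as cover for 51/569 = 8.96% drop-out would also be no improvement, since it would replace the investigators' planning assumption with a rate worked backwards from the total.

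**Conclusion.** No change is needed, because there is nothing to gain from one. The figure of 569 agrees with the sentence's own wording. On the stricter convention it is 7 patients below 576 (7/576 = 1.2%) and about 6 evaluable patients below 518, which moves power from 80.05% to 79.6%. That still rounds to the 80% the plan claims, and it is small beside the effect of the drop-out rate turning out a few points higher or lower than the 10% expected.

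The shortfall rests on two assumptions that the document does not settle: that the 10% is a share of enrolled patients, and that every drop-out leaves the primary analysis. If either fails, the gap shrinks or disappears. The power figures use the plan's own detection rates and one-sided test. With 569 kept as the target, a different description of the drop-out allowance would leave the test, the conduct of the trial and the interpretation of its result as they are.

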A randomized trial comparing the adenoma detection rates between EndoRings colonoscopy (EC) and Standard colonoscopy (SC).

NCT03418662

A randomized trial comparing the adenoma detection rates between EndoRings colonoscopy (EC) and Standard colonoscopy (SC).

Primary Investigator:

[name]
Indiana University Hospital
Indianapolis, IN 46202

Introduction:

During a standard colonoscopy, the folds within the colon can negatively impact the endoscope's view, reducing the ability to detect polyps. In order to help remedy this issue, there is a new provisional device called **ENDORINGS™**. This device is a short silicone rubber tube with flexible circular wings mounted on the tip of the colonoscope to facilitate endoscopic therapy. By flattening the colonic folds during withdrawal, this device could help to keep a suitable depth of the endoscope's view field and, in turn, could prove to increase the adenoma detection rate. The EndoRings is designed to fit specific endoscopes (as designated on the packaging), supplied sterile and is single use only. This device could prove to be an improvement of the current design.

Methods:

Colonoscopies will be performed by [name] and a number of sub-investigators. Data that will be assessed from each colonoscopy include the following:

1. APC (Adenoma per Colonoscopy)
2. Total adenomas detected
3. Total polyps detected
4. Polyp detection rate (PDR)
5. PPC (Polyp per Colonoscopy)
6. Effect on re-scope intervals
7. Cecal intubation rate
8. Comparison of the time required to reach the cecum
9. Comparison of the withdrawal and total procedure time
10. Effect of endoscopist experience on potential gain from using EndoRings
11. Patient comfort score
12. Problems encountered with equipment
 - Slippage of Endorings™
 - Difficulty intubating with Endorings™

Objectives:

The primary endpoint of the study will be the adenoma detection rate of the EndoRings Colonoscopy (EC) compared to that of the Standard Colonoscopy (SC). Complications will be recorded, but the study will not be powered for complications.

The study will help to establish a device that will result in improved adenoma detection rates when compared to a standard colonoscope.

Criteria:

Inclusion Criteria:

- Age \geq 18
- Screening or Surveillance Colonoscopy
- Able to provide written informed consent

Exclusion Criteria:

- Prior history of surgical resection of the large intestine
- Known narrow colon or colon stenosis
- Personal history of Colorectal cancer

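### Does the interim look after 200 patients need an explicit bar on comparing adenoma detection by arm?

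*Combined protocol and SAP*

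**What the plan says.** The section Statistical Analysis & Sample Size gives the interim a single sentence: "Interim analysis will be performed after the 200th patient is enrolled to assess device performance and protocol amendment". It does not list the data to be examined, who sees them, or what could be amended. The document contains no interim hypothesis test, stopping boundary, early claim of success or re-estimation of sample size.

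The same section sets out the one planned comparison: "A two group Chi-Square test with a 0.05 one-sided significance level will have 80% power to detect a difference of 10% ADR". Its planning rates are these: "It is assumed that the proportion of patients with at least one adenoma would be 25% with SC and 35% with EC colonoscopy". Under Randomization, "the subject will be randomized in a 1:1 ratio".

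Two other places bear on what device performance could mean. The Methods list includes "Problems encountered with equipment", with slippage and trouble intubating as its sub-items, alongside cecal intubation, procedure times and patient comfort. The Objectives section says: "The study will help to establish a device that will result in improved adenoma detection rates when compared to a standard colonoscope". It also says: "Complications will be recorded, but the study will not be powered for complications".

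**The concern.** Amendment is a stated purpose of the look, and the term it rests on is undefined. The Objectives section describes what the device should achieve in terms of ADR, and the interim sentence stands directly below the ADR sample-size text. A reader could therefore take device performance to mean ADR by arm.

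If it did mean that, two things would be at stake. An amendment could respond to chance, because 200 patients are few for this comparison. And a reader of the final result could not tell whether the conduct of the trial had been changed in the light of its own primary comparison. If a success claim were also allowed at that point without adjustment, the type I error would exceed the stated 0.05.

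**Working it through.** **Inputs.** ADR 25% (SC) and 35% (EC), one-sided 0.05, 80% power, 259 per group (518 in all), 10% drop-out and an interim after 200 enrolled, all from Statistical Analysis & Sample Size; 1:1 allocation from Randomization. An even split of 100 per arm is an assumption, since blocking is not described. The interim counts enrolled patients, so 90 per arm is shown as the case with 10% drop-out.

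**1. The plan's own figure.** Pooled-variance formula without continuity correction, mean rate 0.30:

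n = [1.645 × √(2 × 0.30 × 0.70) + 0.8416 × √(0.25 × 0.75 + 0.35 × 0.65)]² / 0.10² = (1.066 + 0.542)² / 0.01 ≈ 258.6, so 259 per group. Power at 259 is 80.05%. The stated figure reproduces.

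**2. Precision of ADR by arm.** SE = √[(0.25 × 0.75 + 0.35 × 0.65)/n].

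| n per arm | SE | two-sided 95% margin (1.96 × SE) | one-sided 0.05 scale (1.645 × SE) |
|---|---|---|---|
| 100 | 0.0644 | ±12.6 points | ±10.6 points |
| 90 | 0.0679 | ±13.3 points | ±11.2 points |
| 259 | 0.0400 | ±7.8 points | not needed |

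**3. Power if ADR were tested at the look.** With 100 per arm: Φ[(0.10 − 1.645 × 0.0648)/0.0644] = Φ(−0.10) ≈ 46%, where 0.0648 = √(2 × 0.30 × 0.70/100). With 90 per arm it is about 43%. This is weak, but it is not zero information.

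**4. Misleading interim results (exact binomial).** With a true 10-point gain, the observed gain is zero or negative in 7.0% of trials (8.2% with 90 per arm), and below 5 points in 19.6% (23.0%). With 25% in both arms, a gain of 5 points or more appears in 23.1% (21.9%). The 5-point cut is illustrative; the plan contains no such trigger.

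**5. Type I error.** As written there is one test, at the end: 5.0%. If success could be claimed at z > 1.645 at either look, the correlation between the two statistics is √(200/518) = 0.621 and the overall error is 8.4%. With 180 evaluable, √(180/518) = 0.589 and the error is 8.5%. This needs a rule the plan does not have.

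**6. What the look can support.** If none of 100 EC patients has an equipment problem, the one-sided 95% upper limit is 1 − 0.05^(1/100) = 3.0% (3.3% with 90). For checking how the device handles, the timing is reasonable.

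**7. The two readings side by side.** Where the document means its endpoint it names it, as adenoma detection rate or ADR, in the Objectives and in the sample-size text. The interim sentence uses a different term. The Methods list contains items that are plainly about how the device performs in use. An ADR look is not excluded, but nothing shows that one is planned.

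**The case for a change.** The strongest case for a change is that it costs little and depends on timing. A sentence limiting the look to equipment, complications and pooled ADR would leave alpha, power, 259 and 569 untouched. It would also have to be written before the look, because text added later cannot show that an amendment was independent of the primary comparison. If the sponsor means equipment only, the sentence merely records that intent.

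Part of this stands. The term is undefined, the sentence is complete as it appears, and nobody can establish from the text alone that ADR by arm will stay unseen. If it were used, it would be a weak basis for an amendment.

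The rest does not carry. Imprecision alone is no reason to prohibit an arm-level look, since every interim estimate is less precise than the final one. To say that the look cannot separate a 10-point gain from none overstates 46% power. The figures of about 20% to 23% depend on a cut the plan does not use. No bias, loss of power or inflated error in the final test has been shown for any amendment the plan describes, because it describes none. A bar on ADR alone would also gain little: polyp detection, adenomas per colonoscopy and polyps per colonoscopy by arm are close proxies and would stay open, and the question of who sees the results would remain.

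**Conclusion.** No change to the plan is called for. The interim sentence is brief and leaves a term undefined, but followed as written the plan still yields one final comparison at a one-sided 5.0%, with 80% power at 259 per group. The natural reading, a check on equipment and handling, fits the Methods list and suits 200 patients.

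The ±12.6-point margin (±10.6 on the plan's one-sided scale) and the 46% power describe a use of the look that the plan does not state. The 8.4% describes an early claim of success that it does not state either.

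This rests on three assumptions: about 100 patients per arm at the look, ADR near the planned 25% and 35%, and no claim of success before the final analysis. If an early between-arm success test were in fact intended, the last assumption would fail and the conclusion would have to be revisited.
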